#### **9.2.4 Time-to-Event Endpoint**

For the time from randomization to first occurrence of respiratory failure or death on study due to any cause up to Day 28, the Kaplan-Meier method will be applied. Subjects will be censored at the time of last follow-up. For each group, the 25th percentile, median and 75th percentile will be presented, if possible. Treatment differences between groups will be assessed by the log-rank test.

#### **9.3 Exploratory Endpoints**

For the following exploratory endpoints, descriptive statistics will be presented by treatment group and study day. The changes from baseline to each subsequent day will be calculated for each subject and descriptive statistics will be presented. Treatment differences between groups will be assessed using a mixed-effects model for repeat measures (MMRM). The model will include group, study day as fixed effects, baseline value as a covariate, interaction between study day and group, interaction between study day and baseline, and subject as a random effect.

- Change from baseline in absolute lymphocyte counts at Days 3, 5, 7, 10, 14, 28
- Change from baseline in serum ferritin at Days 3, 5, 7, 10, 14, 28
- Change from baseline in vascular endothelial growth factor (VEGF-A) at Days 3, 5, 7, 10, 14, 28
- Change from baseline for inflammatory cytokines (IL-6, TNF- $\alpha$ , IFN $\gamma$ , IL1 $\beta$ , IL-7, IL-8, IL-10, IL-12, IL-17, IL-18, IP-10) at Days 3, 5, 7, 10, and 28

### **10.0 SAFETY EVALUATION**

#### **10.1 Adverse Events**

Treatment-emergent adverse events (TEAE) will be defined as any AE occurring post first administration of study drug. AEs will be coded using the MedDRA dictionary.

A summary of TEAEs will be presented as the number and percentage of subjects with at least one of the following:

- Any AE
- Any TEAE
- TEAE by Severity
- TEAE by Causality
- TEAEs leading to study discontinuation

- TEAEs leading to death (with outcome of Fatal)
- SAEs
- SAEs by Causality

AEs and TEAEs will be summarized by SOC and preferred term by treatment group. For subjects with the same SOC and preferred term occurring more than once, the first occurrence will be tabulated. AEs and TEAEs will also be presented for each preferred term by maximum severity, by nearest relationship to study drug, and for serious AEs.

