Subjects who discontinue at any time after randomization will not be replaced. There is no treatment crossover in this study.

Once subjects provide informed consent, they will have screening assessments performed (up to a 7-day screening window). Study Day 1 is the day of randomization. Subjects randomized should receive their first dose of STI-5656 or placebo on the day they are randomized (Day 1).

Subjects will be assessed daily while hospitalized. Subjects in both arms are assessed for adverse events and toxicities and all adverse events should be reported regardless of treatment arm assignment or causality.

PK samples will be collected from the first 20 subjects enrolled in this trial. For sampling time points please refer to the schedule of assessments.

Subjects will have an outpatient visit on Day 28 (for various study procedures) and a telephonic contact on Day 60 to collect any additional AEs and follow-up for unresolved AEs to resolution or to establishment of a new baseline.

SOC treatments will be collected in the electronic case report form (e-CRF) until hospital discharge. Continued outpatient treatment (concomitant medications) will be collected until Day 28. Any investigational medication received will be collected until Day 90.

Note: Investigational medicines other than STI-5656 are prohibited up to Day 28 or hospital discharge.

Discharged subjects will be contacted at Day 60 and Day 90 to collect survival, any experimental treatments and additional hospitalization information since the study hospital discharge.

[figure not shown]
Subjects should be encouraged to remain in the study even if Study Drug is discontinued (for any reason).

Statistical Design

An evaluable sample size of 40 subjects per group (treatment arm) will provide 80% power ($\alpha=0.05$, 2-sided) to detect a difference between groups in the number of subjects alive and free of respiratory failure at Day 28. This assumes that 95.7% of subjects who received STI-5656 plus SOC (group 1) and 70% of subjects who received only SOC (group 2) will be alive and free of respiratory failure at Day 28. This represents a treatment effect difference of approximately 26%.

All tests of significance will be assessed at alpha level=0.05, 2-sided.

Figure 1: Study Design

Schedule of Assessments (SOA)

See [Table 1](#) for SOA

Data Monitoring Committee

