4. INVESTIGATIONAL PLAN

4.1. Overall Study Design

This is a Phase 2, randomized, double-blind, placebo-controlled, 2-arm multicenter study to assess the safety and efficacy of oral STI-5656 (or placebo) in the setting of current SOC in subjects with RT-PCR confirmed SARS-CoV-2 infection and COVID-19 pneumonia (documented radiographically) requiring hospitalization. Subjects must have oxygen saturation levels <94% on room air or subject requires supplemental oxygen.

Eighty (80) subjects meeting eligibility criteria will be randomized at a 1:1 ratio to one of two treatment arms in addition to SOC treatments:

- Arm 1: STI-5656
- Arm 2: Placebo

The STI-5656 dose is 100 mg p.o. QD administered up to 14 days or until hospital discharge if sooner.

SOC treatments will be collected in the electronic case report form (e-CRF).

Subjects who discontinue at any time after randomization will not be replaced. There is no treatment crossover in this study.

Once subjects provide informed consent, they will have screening assessments performed (up to 4-day screening window). Study Day 1 is the day of randomization. Randomized Subjects should receive their first dose of Study Drug on Day 1.

Subjects will be assessed daily while hospitalized. Subjects in both arms are assessed for adverse events (AEs) and toxicities and all AEs should be reported regardless of treatment arm assignment or causality. Subjects will be contacted on Day 28 to collect any additional AEs and follow-up for unresolved AEs,

SOC treatments will be collected in the electronic case report form (e-CRF) until hospital discharge. Continued outpatient treatment (concomitant medications) will be collected until Day 28. Any investigational medication received will be collected until Day 90. Note: Investigational medicines other than STI-5656 are prohibited up to Day 28 or hospital discharge.

Discharged subjects will be contacted at Day 60 and 90 to ensure survival and collect any experimental treatments and additional hospitalization information since the study hospital discharge. Subjects on Treatment Arm 1 (STI-5656) should be encouraged to remain in the study even if Study Drug is discontinued (for any reason).

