6.3. Stopping Rule Triggers

Study drug dose should be paused per the guidelines in [Table 2](#) (using the Common Terminology Criteria for Adverse Events, Version 5.0 [CTCAE] for severity grading).

Table 2: Stopping Rule Triggers

If any of the following possibly related AEs occur:	At the first occurrence of any of the stopping rule triggers, discontinue Study Drug for the affected subject and pause further enrollment until DMC deliberations have been completed and a DMC decision that enrollment may be restarted has been rendered.

 • \geq Grade 3 (G3) non-hematologic toxicities • \geq G3 alanine aminotransferase (ALT) elevation OR \geq any ALT and total bilirubin elevation in combination which meet Hy's Law criteria [i.e., any \geq G3 hepatic impairment] • G3 thrombocytopenia with bleeding • G4 thrombocytopenia • G4 neutropenia • G3 neutropenia or thrombocytopenia in > 3 subjects • \geq G3 renal impairment including acute kidney injury requiring hemodialysis • Any SUSAR (suspected unexpected serious adverse reaction) 	

A DMC teleconference will be arranged within 5 business days of the stopping rule trigger. This should provide sufficient time for the CRO to prepare a blinded summary of the AE and the independent statistician to arrange to be unblinded to assist the DMC in its deliberations.

Additionally, the DMC will be provided with tabular safety summaries at 25%, 50% and 75% enrollment for ongoing surveillance.

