9.4. Data Analysis

9.4.1. Subject Disposition

The number and percentage of subjects included in each population, who completed the study, who discontinued study and reason for discontinuation will be presented for each cohort and treatment.

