10.2.5. Action Taken

The Investigator will report the action taken with investigational product as a result of an AE or SAE, as applicable (e.g., discontinuation, interruption, or reduction of study treatment, as appropriate) and report if concomitant and/or additional treatments were given for the event.

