## 8.0 STATISTICAL ANALYSES

### 8.1 Subject Disposition

The number of percentage of subjects in screened, randomized, FAS population, Safety Population, PP Population, completed the study and discontinued from the study will be reported, along with the reason for discontinuation.

Percentages will be out of the number of safety population. Counts only will be reported for screened subjects.

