## **8.6 Study Drug Administration**

Two STI-5656 or matching placebo capsules p.o. QD (two 50-mg capsules) are administered orally up to 14 days or until hospital discharge if sooner. If vomiting occurs within 30 minutes after a patient takes the dose and the patients can tolerate the medication, the vomited dose should be made up.

If the subject is unable to swallow, the capsule contents may be flushed down a nasogastric or feeding tube with water.

For study drug administration, descriptive statistics of the following parameters will be presented.

- Number of days on study treatment
- Total dose planned
- Total dose administered
- Total dose missed
- Compliance rate, defined as the total dose administered/total dose planned, expressed as a percentage.

Subject listing of study drug administration will be presented.

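### No planned summary counts, by arm, the subjects whose study drug was stopped or interrupted because of an adverse event; the SAP counts only adverse events leading to study discontinuation

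*SAP*

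**What the plan says.** **Safety action.** Protocol 6.3, Table 2, lists possibly related toxicities. At the first trigger the instruction is to "discontinue Study Drug for the affected subject and pause further enrollment until DMC deliberations have been completed". It does not withdraw the subject from the study.

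**After drug is stopped.** The protocol synopsis states: "Subjects should be encouraged to remain in the study even if Study Drug is discontinued (for any reason"). Protocol 4.1 repeats this only for Arm 1 subjects, who "should be encouraged to remain in the study even if Study Drug is discontinued (for any reason").

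**What is recorded.** Protocol 10.2.5: "The Investigator will report the action taken with investigational product as a result of an AE or SAE", with discontinuation, interruption and reduction given as examples.

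**What is summarised.**
- SAP 10.1, overview table: "TEAEs leading to study discontinuation". There is no row for stopping or interrupting study drug.
- SAP 8.1: the numbers of subjects who "completed the study and discontinued from the study will be reported, along with the reason for discontinuation".
- Protocol 9.4.1: those "who discontinued study and reason for discontinuation will be presented for each cohort and treatment".
- SAP 8.6: "Number of days on study treatment", then planned, administered and missed dose and a compliance rate, plus a subject listing. No reason for stopping is mentioned.

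SAP 1.0 says that its analyses override those in the protocol.

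**The concern.** Safety and tolerability is a secondary objective in both documents. A direct measure of tolerability is the number of subjects in each arm who could not continue the drug because of an adverse event. The plan keeps leaving the drug and leaving the study apart in conduct, then summarises only the second. A subject managed as the protocol asks, with drug stopped for toxicity and follow-up continued, adds nothing to the one row that concerns discontinuation. The better the sites retain such subjects, the smaller the row becomes. A difference between arms in that row could also reflect different retention after stopping rather than different tolerability.

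**Working it through.** The plan attaches no figure to this point, so the check is a tracing exercise, followed by two small illustrations on assumed inputs.

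**1. Trace one subject.** Drug is stopped under Table 2, and the subject stays in follow-up to Day 90.

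| Planned summary | What this subject contributes |
|---|---|
| SAP 10.1, TEAE by severity, by causality, by SOC and preferred term, serious AEs | The event is counted |
| SAP 10.1, study-discontinuation row | 0 |
| SAP 8.1, discontinued from study, with reason | 0 |
| SAP 8.6, days on treatment, missed dose, compliance | Shorter exposure, no reason |
| SAP 10.2, laboratory shifts | Any laboratory change, without the drug action |
| Protocol 9.4.4, list of AE tables | Event counted; no row by drug action |

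The event is visible; that it ended treatment is not.

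**2. Can SAP 8.6 supply the missing count?** Dosing runs to Day 14 or to discharge if sooner. Assume one dose a day and take two subjects who each receive 5 doses (an assumed number). Subject A stops for toxicity and stays in hospital past Day 14. Subject B is discharged after the fifth dose.

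Compliance = administered / planned.

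- If planned dose ends at discharge: A has 14 planned, 14 − 5 = 9 missed, compliance 5/14 = 35.7%. B has 5 planned, 0 missed, compliance 5/5 = 100%. The two are separated.
- If planned dose is always 14: both have 9 missed and 35.7%. They cannot be told apart.

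The SAP does not define planned dose. Even under the first definition, A looks the same as a subject whose dosing ended because feeding-tube administration was not feasible (Protocol 6.4), or who missed doses for some other reason. In both cases days on treatment is 5 for A and for B. SAP 8.6 therefore recovers part of the signal, but not the count.

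**3. How far can the row fall short?** Let k be the subjects in an arm whose drug is stopped for an AE, and r the share of them who stay in the study. Assume that those who leave do so because of that AE. Then:

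row count = k(1 − r), shortfall = k·r

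With 40 per arm, one subject is 1/40 = 2.5 percentage points. No document gives k or r. For illustration only, take k = 6 on active (6/40 = 15.0%) and k = 1 on placebo (1/40 = 2.5%):

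| Retention r | Active row (expected) | Placebo row (expected) | Difference |
|---|---|---|---|
| 0 | 6 (15.0%) | 1 (2.5%) | 12.5 points |
| 0.5 | 3 (7.5%) | 0.5 (1.25%) | 6.25 points |
| 1 | 0 (0.0%) | 0 (0.0%) | 0 points |

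The true difference in drug stops is 15.0 − 2.5 = 12.5 points on every line; only retention changes.

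**The case against.** The strongest reply is that nothing important disappears. Nearly every Table 2 trigger is a related event of Grade 3 or higher or a SUSAR, and SAP 10.1 tabulates TEAEs by severity, causality, preferred term and seriousness. In the illustration, the 6 and 1 subjects would show up in neighbouring rows of the same overview table. This stands. A reader might infer that safety-driven stops vanish from the report, or that the drug would look well tolerated whatever its toxicity; the documents do not support that.

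Missed dose and compliance also carry some information, as step 2 shows. This stands in part, subject to how planned dose is defined.

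A row of zero in both arms needs every affected subject to stay. The protocol only encourages staying, so zero is the extreme of a range and not a prediction.

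Listings are planned, and 80 subjects can be read one by one. A listing is still not a count by arm, and SAP 8.6 does not say that its listing will link a stop to an event. Review of triggers and periodic safety tables by the DMC protects subjects during the trial, but does not supply this count in the final analysis.

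Finally, the SAP may have used study discontinuation loosely to mean drug discontinuation. The protocol separates the two, and Protocol 8.1.10 has study discontinuation registered in the IRT. If drug discontinuation was meant, the row still needs rewording.

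**Conclusion.** The point holds as a reporting gap. As written, no summary gives, by arm, the number of subjects whose study drug was stopped or interrupted because of an adverse event, and the one discontinuation row varies with study retention. Toxicity itself remains visible in the other adverse-event tables and, in part, in the exposure table.

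The size is 2.5 percentage points per arm of 40 for each stop followed by continued participation. The total cannot be stated, because the documents give neither a stop rate nor a retention rate; the 15.0% against 2.5% example is assumed. The conclusion rests on reading SAP 10.1 and 8.1 literally, and on subjects following the request to stay. It touches no efficacy result, error rate or power. The change is worth making because it serves a stated objective at very low cost.

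A reader might also infer that a full table of reasons for ending treatment could be built without new data. That is not established. The action taken is required for each AE, but no section states that a general reason for ending treatment is collected; the IRT text covers study completion and discontinuation only.

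**What to change.** 1. In SAP 10.1 add two rows, TEAEs leading to discontinuation of study drug and TEAEs leading to interruption of study drug, overall and by SOC and preferred term, by arm. Derive both from the action-taken item in Protocol 10.2.5. Keep the study-discontinuation row.
2. In SAP 8.1 or 8.6, where the data allow, separate treatment ended by discharge, by completing 14 days or by death from treatment ended by an AE. Confirm first whether the eCRF holds a reason for ending treatment; if it does not, limit the table to what can be derived from dates and the action-taken item.
3. In SAP 8.6 define planned dose, stating whether it ends at discharge and at death.
4. Reconcile the wording on which the rows depend. The sentence introducing Table 2 speaks of pausing the drug, while the table speaks of discontinuing it. The synopsis asks all subjects to stay in the study, while Protocol 4.1 asks only Arm 1. The sponsor should settle which reading applies.

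Items 1 and 3 cost a few table rows and some SAP wording, with no new data. Item 2 may be limited by the eCRF. Item 4 is a protocol clarification. The SAP changes are best made before unblinding; if made later, SAP 11.0 requires them to be described and justified in the study report.

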## **10.2 Laboratory Results**

For each continuous laboratory parameter (chemistry, coagulation, hematology), descriptive statistics will be presented for each study day collected and for the changes from baseline for by treatment group.

Categorical urinalysis parameters will be presented as the number and percentage of subjects per category for each study day collected by treatment group.

For laboratory parameters with normal ranges, the shift from Baseline (low, normal, high) to each subsequent study day (low, normal, high) will be presented by treatment group.

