9.4.4. Secondary Endpoints (Safety)

AEs will be coded using the Medical Dictionary for Regulatory Activities (MedDRA) and will be summarized by System Organ Class (SOC) and Preferred Term for each group. The first occurrence will be tabulated for an event that occurred more than once for a subject.

Additionally, AEs will be tabulated by maximum severity and nearest relationship to IP. SAEs will be summarized similarly to AEs.

For continuous safety endpoints, descriptive statistics (number of subjects, mean, standard deviation, minimum, median and maximum values) will be presented by group and study day. The changes from Day 1 to each subsequent day will be calculated for each subject and descriptive statistics will be presented. Possible differences between groups will be assessed using a mixed effect model repeat measurement (MMRM) analysis of covariance. The model will include the Day 1 value as a covariate, fixed effects of group, study day and group-by-study day interaction with subject as a random effect.

Categorical safety endpoints will be summarized as the number and percentage of subjects per category for each group.

Treatment-emergent adverse events (TEAE) will be defined as any AE occurring post first administration. Adverse events will be presented for each cohort and treatment by System Organ Class (SOC) and Preferred Term (PT):

- Treatment-emergent adverse events (TEAE): defined as any AE occurring postdose administration through 28 days following IP administration.
- IP related TEAEs
- SAEs
- IP related SAEs
- TEAEs (by grade and relationship to IP)
- Laboratory abnormalities by toxicity grade

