10.3. Abnormal Laboratory Values

An abnormal laboratory value is considered to be an AE if the abnormality:

- results in discontinuation from the study; or
- requires treatment, modification/ interruption of study treatment dose, or any other therapeutic intervention; or
- is judged to be of significant clinical importance

Regardless of severity grade (per CTCAE version 5.0), only laboratory abnormalities that fulfill a seriousness criterion need to be documented as a serious adverse event.

If a laboratory abnormality is one component of a diagnosis or syndrome, then only the diagnosis or syndrome should be recorded on the AE page/screen of the CRF. If the abnormality was not a part of a diagnosis or syndrome, then the laboratory abnormality should be recorded as the AE.

If possible, the laboratory abnormality should be recorded as a medical term and not simply as an abnormal laboratory result (eg, record thrombocytopenia rather than decreased platelets).

Adverse Laboratory values that also meet the definition of SERIOUS, will be reported as SAEs.

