## **1.0 INTRODUCTION OF THE STATISTICAL ANALYSIS PLAN**

The statistical analysis plan (SAP) is based on protocol STI-5656-2001 ‘A Phase 2, Randomized, Double-Blind, Placebo-Controlled Study of The Safety and Efficacy of Sti-5656 (Abivertinib Maleate) In Subjects Hospitalized Due to Covid-19’, V5.0 dated 07Dec2020. It details the methodology to be used in analyzing the data and outlines the specifications in the Tables, Figures and Listings (TFLs) for data to be included for executing the final statistical analyses for this study.

PK analysis is not included in this plan.

The analyses specified in this document supersede any high-level analysis plan described in the protocol.

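### SAP 10.2 omits the protocol's laboratory table by toxicity grade, so Grade 3-4 values not reported as adverse events would not be counted by arm

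*SAP*

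**What the plan says.** Protocol 9.4.4 closes with a list of safety presentations. Adverse events by grade and relationship form one item, and "Laboratory abnormalities by toxicity grade" is a separate item.

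SAP 10.2 plans three laboratory outputs:
- "For each continuous laboratory parameter (chemistry, coagulation, hematology), descriptive statistics will be presented for each study day collected", with changes from baseline;
- counts for categorical urinalysis parameters;
- for parameters with normal ranges, "the shift from Baseline (low, normal, high) to each subsequent study day (low, normal, high".

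Neither toxicity grade nor CTCAE is mentioned anywhere in the SAP. SAP 1.0 states: "The analyses specified in this document supersede any high-level analysis plan described in the protocol". SAP 11.0 does not list the missing table as a change.

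Protocol 6.3 writes its triggers in CTCAE v5.0 grades. At or above the stated grade they include "G3 alanine aminotransferase (ALT) elevation" and "G3 renal impairment including acute kidney injury requiring hemodialysis", together with an ALT and bilirubin combination and Grade 3 or 4 neutropenia and thrombocytopenia. Each trigger is an adverse event judged possibly related.

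Protocol 10.3 decides when a laboratory value becomes an adverse event. It opens "An abnormal laboratory value is considered to be an AE if the abnormality" and then gives the conditions: discontinuation from the study; a need for treatment, dose modification or interruption, or another intervention; or a judgment of clinical importance. Where the abnormality belongs to a diagnosis or syndrome, only the diagnosis or syndrome is entered.

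**The concern.** Safety and tolerability are a secondary objective, and the protocol's own thresholds for liver, kidney and blood counts are expressed in grades. A reader of the final report will want to know how many subjects in each arm reached those grades on the measured values, whether or not an investigator reported an event. The protocol planned a table for this and the SAP does not. If nothing else fills the gap, an imbalance in unreported Grade 3-4 values could pass unseen. There would also be no objective check on how completely laboratory events were reported.

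**Working it through.** The plan gives no figure on this point, so there is none to reproduce. The check compares the outputs and asks what each can recover.

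**Step 1: outputs side by side.**

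| Question, by arm | Protocol 9.4.4 | SAP |
|---|---|---|
| Adverse events by severity grade | Yes | Yes (10.1, preferred term by maximum severity) |
| Laboratory values by day, descriptive | Yes | Yes (10.2) |
| Low/normal/high shift by day | Not listed | Yes (10.2) |
| Laboratory values by toxicity grade | Yes | No |

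**Step 2: can the shift table stand in for grades?** Take three subjects with ALT as a multiple of the upper limit of normal (ULN), classed high if above 1. The values are illustrative assumptions.
- Set A, baseline to post-baseline: 1.5 to 1.6, 0.8 to 1.2, 0.9 to 1.3.
- Set B: 1.5 to 12, 0.8 to 8, 0.9 to 25.

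Both sets give normal to high = 2 and high to high = 1. The tables are identical although the post-baseline values are 1.2 to 1.6 times ULN in one and 8 to 25 times ULN in the other. The same holds downward, because every degree of neutropenia or thrombocytopenia falls in the low cell.

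High-to-high cases can occur here. Exclusion 4 in Protocol 5.2 joins its ALT and bilirubin limits with 'and', so raised ALT alone does not exclude a subject. Such a subject stays high to high however far ALT climbs.

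**Step 3: do the descriptive statistics and listings recover the count?** In part. The daily maximum separates set A (1.6) from set B (25). Now take set C: 1.5 to 1.6, 0.8 to 1.2, 0.9 to 25. Sets B and C share the same shift table and the same maximum of 25, yet B has three subjects with values of 8 or more and C has one. The means differ, (12 + 8 + 25)/3 = 15.0 against (1.6 + 1.2 + 25)/3 = 9.3, but a mean does not give the number of subjects per grade.

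Three further limits apply.
- The tables are by day, so peaks on different days cannot be assigned to the same or different subjects.
- ALT and bilirubin are summarized separately, so their joint elevation is not visible.
- The list of statistics in SAP 7.2 names the maximum but mentions the minimum only in its rounding rule, and low counts need the minimum.

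Listings would let a reader count by hand, but they are not a summary by arm.

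**Step 4: do the adverse event tables recover the count?** For a trigger recorded as a possibly related adverse event, yes: SAP 10.1 shows it by preferred term, maximum severity and relationship. Two groups of Grade 3-4 values remain:
- values that met none of the Protocol 10.3 conditions listed above;
- values entered only under a diagnosis or syndrome, which appear under that term with that term's severity.

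These two groups are the residual loss.

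**The case against.** The strongest reply is that the events of most interest are still reported. Every stopping-rule trigger is by definition an adverse event, and SAP 10.1 tabulates adverse events by maximum severity and by arm. A value acted on under Protocol 6.3 leads to discontinuation of study drug, which appears to satisfy the dose-change condition in Protocol 10.3. SAP 10.2 also gives daily statistics, and SAP 7.2 adds maxima and subject listings. The DMC works case by case and receives its own safety summaries at 25%, 50% and 75% enrollment, so it does not depend on these tables. All of this stands, and it narrows the point.

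It does not remove it. Protocol 9.4.4 lists graded adverse events and graded laboratory abnormalities as two outputs, so the protocol did not treat one as a substitute for the other. The graded laboratory table is the one that does not depend on an investigator's judgment of relatedness or importance.

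A reader might infer more than the documents support:
- That the final tables cannot show stopping-rule events by arm. They can, where the event is recorded as an adverse event.
- That the SAP deliberately withdrew the table. It is silent, and replacement is inferred only from the clause in SAP 1.0.
- That many baselines are already high, so most worsening is hidden. No figure in the documents supports this, and the eGFR exclusion in Protocol 5.2 limits it for renal function.
- That the stopping rule is weakened. It does not use these tables.

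**Conclusion.** The point holds as a gap in final safety reporting. SAP 10.2 leaves out an output listed in the protocol, and the low/normal/high shift it offers carries no grade information. Grade 3-4 laboratory values that are not adverse events under Protocol 10.3, or that are entered only under a diagnosis, would not be counted by arm. The check of adverse event reporting against measured values is also lost. The primary analysis and DMC monitoring are unaffected.

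The number of subjects involved cannot be derived from the documents; it depends on how sites apply Protocol 10.3.

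The conclusion rests on two assumptions. The first is that the SAP's silence means the table is not planned. The second is that protocol V5.0 keeps the item: the SAP is based on "V5.0 dated 07Dec2020", while the protocol supplied is Version 4.0. If V5.0 dropped the item, the discrepancy between the documents disappears, but the limitation of the SAP 10.2 tables remains.

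**What to change.** In SAP 10.2, restore the laboratory table by CTCAE v5.0 grade and by arm. Present it as baseline grade against worst post-baseline grade per subject, for the stopping-rule parameters that can be graded from the laboratory data: ALT, total bilirubin, creatinine, platelets and neutrophils, in the high or low direction as applicable. Add a count by arm of subjects with combined ALT and total bilirubin elevation. Write its definition into the SAP, because Protocol 6.3 names Hy's Law without numerical limits.

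The protocol promises only abnormalities by grade. The baseline-to-worst format and the combined count go a step further and are recommended because they answer the question directly. If the sponsor prefers not to produce a graded table, the SAP should record and justify its omission as a change from the protocol. In either case, confirm what V5.0 says.

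The cost is one or two extra tables plus programming of the grades. Hematology and chemistry are already collected daily until discharge, so no new data or procedures are needed.
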